6.2.5. Sensitivity Analyses of the Primary Efficacy Analysis

[figure not shown]
6.2.5.1. Sensitivity Analysis #1: Assuming MAR missing data mechanism for all ICE's

In order to assess the robustness of the underlying assumptions with respect to the ICEs and ET occurring during the efficacy period (Period 1), analysis of the primary efficacy estimand will be repeated assuming MAR for all ICEs.

6.2.5.2. Sensitivity Analysis #2: 'Tipping Point' analysis

To assess the robustness of the underlying missing data assumptions, a tipping point analysis will be conducted under a range of missing data assumptions, to determine how extreme assumptions would need to be for any conclusion of superiority of active treatment compared to placebo to change. Assumptions about missing values on active and placebo arms will vary independently and will include scenarios where subjects with missing data on the active treatment group have worse outcomes than subjects with missing data on placebo group and vice versa.

For each pair of offset values applied to active treatment and placebo groups, a point estimate, 95% CI and p-value will be calculated, to obtain a combination of offset values at which the overall analysis becomes non-significant (i.e., the "tipping point").

6.2.6. Sub-Group Analysis

Subgroup analyses of the primary efficacy endpoint will be performed by region, sex and time from diagnosis of schizophrenia (<5 year, 5-10 year and 10 years or more), race, ethnicity and prior use of Olanzapine. The subgroup analyses will be performed on the primary efficacy estimand. For a given subgroup analysis, each group must have at least 16 patients.

6.3. Key Secondary and Other Secondary Efficacy Endpoints and Analysis

This section will describe the secondary efficacy endpoints and methods used for analysis of each of the secondary efficacy endpoints. As described in Section 1.1 the following key secondary endpoints will be analyzed:

- Change in Clinical Global Impression-Severity (CGI-S) scale score from baseline to week 8
- Change in Personal and Social Performance Scale (PSP) score from baseline to week 8

And the following other secondary efficacy endpoints:

- Change from baseline to weeks 1, 2, 4 and 8 in the PANSS total score
- Clinical Global Impression-Improvement (CGI-I) scale at weeks 4 and 8
- Clinical Global Impression-Severity (CGI-S) scale at weeks 1, 2, 4 and 8
- Patient Global Impression-Improvement (PGI-I) scale at weeks 2, 4 and 8
- Change from baseline to weeks 4 and 8 in the Schizophrenia Quality of Life Scale (SQLS)
- Change from baseline to weeks 4 and 8 in the PSP score

The definition of each of the endpoints described above and the analysis method are described in detail in the following sections (Section 6.3.1 - Section 6.3.8)

The methods that will be used for secondary efficacy endpoints are described in Section 6.2.

By-visit analyses for the PANSS, CGI-S and PSP endpoints will be performed based on their respective estimands in addition to using the treatment policy and modified treatment policy estimands shown in [Appendix D](#).

All other secondary efficacy endpoints will be analyzed using only the treatment policy and modified treatment policy estimand shown in [Appendix D](#).

6.3.1. Clinical Global Impression-Severity (CGI-S) – Change from Baseline to Week 8

6.3.1.1. Definition

The investigator/trained rater will complete the CGI-S at the time points specified in Table 1 and Table 2 of the study protocol. The CGI-S allows the rater to assess the patient's current severity of illness on a scale of 1 to 7, where 1=normal/not at all ill, 2=borderline mentally ill, 3=mildly ill, 4=moderately ill, 5=markedly ill, 6=severely ill, and 7=among the most extremely ill patients.

6.3.1.2. Analysis

Model Specification

Analysis will be conducted following the same steps as described in Section 6.2.4 except that the outcome variable will instead be the change from baseline in CGI-S score.

6.3.2. Personal and Social Performance Scale (PSP) Score – Change From Baseline to Week 8

6.3.2.1. Definition

The PSP will be administered to patients at the time points specified in Table 1 and Table 2 of the study protocol. The PSP is a clinician-rated instrument that measures personal and social functioning in patients with schizophrenia. The PSP is a 100-point single-item rating scale, divided into 10 equal intervals. The score is based on the assessment of patient's functioning in 4 categories: 1) socially useful activities, including work and study; 2) personal and social relationships; 3) self-care; and 4) disturbing and aggressive behaviors. Higher scores represent better personal and social functioning, with ratings from 91 to 100 indicating more than adequate functioning, while scores under 30 indicate functioning so poor that intensive supervision is required.

6.3.2.2. Analysis

Analysis will be conducted following the same steps as described in Section [6.2.4](#) except that the outcome variable will instead be the PSP score.

6.3.3. PANSS Total Score – Change From Baseline to Weeks 1, 2, 4 and 8

By visit analysis of change from baseline will be conducted based on the treatment policy, in addition to the by visit analyses based on the primary efficacy estimand. A mixed model repeated measures (MMRM) analysis will be performed using the PANSS total score and change in PANSS total score from baseline as the dependent variable, and treatment arm, study visit, treatment-visit interaction, stratification variables (sex and geographic region), age, and PANSS total score at baseline (only for the change from baseline model) as covariates. An unstructured covariance matrix will be used in all models. Analyses will be performed in SAS using the Kenward-Roger option to estimate the denominator degrees of freedom and standard errors.

6.3.4. Clinical Global Impression-Improvement (CGI-I) scale – At Weeks 4 and 8

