1.1. Primary and Secondary Study Objectives and Endpoints

The primary and secondary study objectives and endpoints are:

Objectives	Endpoints
The primary objective is to evaluate the efficacy of TV-44749 in adult patients with schizophrenia.	
The primary efficacy endpoint is as follows:
 
 • The change from baseline to week 8 in the Positive and Negative Syndrome Scale (PANSS) total score.
A key secondary objective is to further evaluate the efficacy of TV-44749 based on additional parameters in adult patients with schizophrenia.	
The secondary efficacy endpoints are as follows:
 
 • Change in Clinical Global Impression-Severity (CGI-S) scale score from baseline to week 8 • Change in Personal and Social Performance Scale (PSP) score from baseline to week 8
A secondary objective is to evaluate the safety and tolerability of TV-44749 in adult patients with schizophrenia.	
The safety and tolerability endpoints will include, where appropriate, the following: adverse events (including serious adverse events, extrapyramidal symptoms, injection pain and other injection site reactions [local tolerability]), vital signs (blood pressure, pulse and orthostatic changes, and temperature), body weight, laboratory tests, electrocardiogram (ECG), concomitant medication use, time to all-cause discontinuation, all-cause discontinuation rates and discontinuation rates due to adverse events (tolerability), and the following rating scales:
 
 • Abnormal Involuntary Movement Scale (AIMS) • Simpson-Angus Scale • Barnes Akathisia Rating Scale • Columbia Suicide Severity Rating Scale (C-SSRS) • Calgary Depression Scale for Schizophrenia (CDSS)
A secondary objective of this study is to evaluate the efficacy of TV-44749 from baseline to endpoint in Period 1 in adult patients with schizophrenia.	
 • Change from baseline to weeks 1, 2, 4 and 8 in the PANSS total score • Clinical Global Impression-Improvement (CGI-I) scale at weeks 4 and 8 • Clinical Global Impression-Severity (CGI-S) scale at weeks 1, 2, 4 and 8 • Patient Global Impression-Improvement (PGI-I) scale at weeks 2, 4 and 8 • Change from baseline to weeks 4 and 8 in the Schizophrenia Quality of Life Scale (SQLS) • Change from baseline to weeks 4 and 8 in the PSP score

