1.2.2. Key Secondary Efficacy Estimand

For the key secondary efficacy objectives, attributes “a” and “b” will be implemented in the same manner as planned for the primary estimand:

- a. Treatment:** The treatment of low, medium, or high dose of TV-44749 compared to placebo, separately, will be evaluated according to the randomization assignment at Period 1.
- b. Population:** All randomized adult patients who have a confirmed diagnosis of schizophrenia, present with acute exacerbation of disease, and are eligible for olanzapine treatment.
- c. Endpoint:** Change in Clinical Global Impression-Severity (CGI-S) scale score from baseline to week 8 and change in Personal and Social Performance Scale (PSP) score from baseline to week 8.
- d. Population-level summary:** Details are described in Section 6.4.

Any data collected after the ICE of taking prohibited antipsychotic medications (that is not short term) or withdrawal from randomized treatment due to insufficient clinical response (lack of efficacy) will be regarded as patients not reaching the optimal treatment effect (ie, MNAR). The ICE of early discontinuation for other reasons will be regarded as if the patient fully complied and completed the study (assuming MAR); see Table 1 for further details on the classification and handling of ICEs. This complies with the hypothetical approach.

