6.2.4. Primary Analysis

For each of the 200 complete datasets, a mixed model repeated measures (MMRM) analysis will be performed using the change in PANSS score from baseline to week 8 as the dependent variable, and treatment arm, study visit, treatment-by-visit interaction, stratification variables (sex and geographic region), age, and PANSS total score at baseline as covariates. An unstructured covariance matrix will be used in all models. Analyses will be performed in SAS using the Kenward-Roger option to estimate the denominator degrees of freedom and standard errors. If the group size of stratification factors is small, groups may be pooled together for modeling purposes. Such a decision will be made prior to unblinding and documented in the statistical data review meeting.

Least squares means will be calculated of the change from baseline to week 8 in the PANSS total score for each of the 4 treatment arms and for the differences between each of the TV-44749 arms and the placebo arm. In addition, the 95% confidence intervals, and the nominal p-values

for the comparisons between each of the 3 dose strengths of TV-44749 and placebo will be calculated using PROC MIANALYZE using Rubin's rules (see [Appendix B](#) for further details and example code). The nominal p-values will be adjusted for multiplicity (see Section [7](#)).

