6.4.1.2. Analysis

MMRM model will be repeated for this endpoint

```
proc mixed data=data method=reml;
  class trt01pn avisitn subjid;
  model variable = trt01pn avisitn trt01pn*avisitn sex region age
baseline/ddfm=kr cl;
  repeated avisitn/subject=subjid type=un;
  lsmeans trt01pn*avisitn/cl;
run;
```

Results Presentation

Summary statistics will be produced for absolute and change from period 2 baseline, by timepoint and treatment (TV-44749 318mg, TV-44749 425mg, TV-44749 531mg and former placebo assignment, i.e., overall 6 groups for period 2)

Least-square means of absolute value and change from baseline, including standard errors and 95% CI, will be presented at each timepoint by treatment group.

6.4.2. Clinical Global Impression-Severity (CGI-S) – Change From Baseline to End of Treatment Period in Period 2

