6.4.2.2. Analysis

MMRM model will be repeated for this endpoint, see Section [6.4.1.2](#).

6.4.3. Personal and Social Performance Scale (PSP) score – Change From Baseline to End of Treatment Period in Period 2**6.4.3.1. Definition**

See Section [6.3.2.1](#).

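### As written, the key secondary CGI-S and PSP models adjust for baseline PANSS rather than their own baseline, and the PSP model names the score although the endpoint is the change

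*SAP*

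**What the plan says.** The primary MMRM in SAP 6.2.4 has treatment, visit, treatment-by-visit interaction and "stratification variables (sex and geographic region), age, and PANSS total score at baseline as covariates". The two key secondary sections point back to it:

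- 6.3.1.2, CGI-S: the same steps, "except that the outcome variable will instead be the change from baseline in CGI-S score".
- 6.3.2.2, PSP: the same steps, "except that the outcome variable will instead be the PSP score".

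In both, the exception covers the outcome only. SAP 6.3 sends the secondary methods back to 6.2 in general terms and adds no rule about own baseline. Section 6.3.5 applies the CGI-S method to the by-visit analysis.

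The declared PSP endpoint is a change. SAP 1.1 lists "Change in Personal and Social Performance Scale (PSP) score from baseline to week 8", and 1.2.2, the heading of 6.3.2 and Appendix D agree.

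Elsewhere the SAP names the matching baseline: CGI-S for CGI-I (6.3.4.2), SQLS for SQLS (6.3.7.2) and PSP for the other-secondary PSP analysis (6.3.8). The Period 2 code in 6.4.1.2 is generic: "model variable = trt01pn avisitn trt01pn*avisitn sex region age", followed on the next line by "baseline/ddfm=kr cl". Sections 6.4.2.2 and 6.4.3.2 repeat that model for CGI-S and PSP.

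**The concern.** A programmer who follows 6.3.1.2 and 6.3.2.2 to the letter fits change in CGI-S, and the PSP score itself, with baseline PANSS as the only baseline-severity term. A scale's own baseline is usually its strongest baseline predictor, so leaving it out discards precision on both key secondary endpoints.

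The omission also makes the PSP outcome wording matter. With own baseline in the model, analysing the score or the change gives the same treatment difference and the same test. Without it they are two different analyses with two different results. Nor is score safe shorthand for change in this SAP: 6.3.3 lists PANSS score and PANSS change as separate dependent variables and uses the baseline covariate only for the change.

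Finally, 6.3.8 reports week 8 PSP change from a model with baseline PSP and without multiple imputation. Two week 8 PSP models with different outcomes and covariates therefore coexist.

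**Working it through.** **No figure to reproduce.** The documents give no SD, correlation or power for CGI-S or PSP, and the effect size and power for the primary endpoint are redacted. The sizes below rest on assumed inputs, for complete data at week 8.

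**Notation.** P = baseline PANSS, Y0 = own baseline, Y8 = week 8 value, with SDs s0 and s8. r = corr(P, Y0), ρ = corr(Y0, Y8), q = corr(P, Y8). Residual variances:

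- Both baselines: s8²[1 − (ρ² + q² − 2rρq)/(1 − r²)]
- Score, PANSS only: s8²(1 − q²)
- Change, PANSS only: s0² + s8² − 2ρ·s0·s8 − (q·s8 − r·s0)²
- Own baseline only: s8²(1 − ρ²)

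Each is divided by the both-baselines value. The increase in standard error is √ratio − 1.

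**PSP.** Assumed s0 = s8 = 1, r = −0.5, ρ = 0.3, 0.5 and 0.7. In scenario 1 PANSS acts only through baseline PSP, so q = −0.5ρ. In scenario 2, q = −0.4.

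| Scenario, ρ | Both | Score, PANSS only (ratio) | Change, PANSS only (ratio) | Own only (ratio) |
|---|---|---|---|---|
| 1, 0.3 | 0.910 | 0.978 (1.074) | 1.277 (1.404) | 0.910 (1.000) |
| 1, 0.5 | 0.750 | 0.938 (1.250) | 0.938 (1.250) | 0.750 (1.000) |
| 1, 0.7 | 0.510 | 0.878 (1.721) | 0.578 (1.132) | 0.510 (1.000) |
| 2, 0.3 | 0.827 | 0.840 (1.016) | 1.390 (1.681) | 0.910 (1.101) |
| 2, 0.5 | 0.720 | 0.840 (1.167) | 0.990 (1.375) | 0.750 (1.042) |
| 2, 0.7 | 0.507 | 0.840 (1.658) | 0.590 (1.164) | 0.510 (1.007) |

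Two rows worked through:

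- Scenario 2, ρ = 0.3. Both: 1 − (0.09 + 0.16 − 0.12)/0.75 = 0.827. Score: 1 − 0.16 = 0.840, ratio 1.016, √1.016 − 1 = 0.8%. Change: 2 − 0.6 − (−0.4 + 0.5)² = 1.390, ratio 1.681.
- Scenario 1, ρ = 0.7. Both: 1 − 0.49 = 0.510. Score: 1 − 0.35² = 0.878, ratio 1.721, √1.721 − 1 = 31.2%.

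**CGI-S.** Assumed s0 = 0.6, 0.65 and 0.7, s8 = 1.1, ρ = 0.2 to 0.5, r = 0.4 to 0.7, and q = rρ or rρ + 0.1. For change with PANSS only the ratio has minimum 1.001, median 1.062 and maximum 1.208. The maximum is at s0 = 0.7, ρ = 0.2, r = 0.4, q = 0.18. There the change variance is 0.49 + 1.21 − 0.308 − (0.198 − 0.28)² = 1.385, and the both-baselines variance is 1.21 × [1 − (0.04 + 0.0324 − 0.0288)/0.84] = 1.147. The ratio is 1.208 and √1.208 − 1 = 9.9%. Own baseline only: at most 1.027.

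**Power illustration.** Take 110 completers per arm (440/4), two-sided 0.05, and an effect set to give 90% power in the own-baseline model. Under scenario 1, PSP score with PANSS only has power 88%, 83% and 70% at ρ = 0.3, 0.5 and 0.7.

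**Score or change.** In one simulated data set with 110 per arm, the treatment difference with own baseline was 0.171 for both outcomes. With PANSS only it was 0.114 for the score and 0.245 for the change.

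**The case against.** **The operative code is not visible.** Section 6.2.4 refers to Appendix B for details and example code. The model blocks there are not readable, nor is the content of Protocol 10.5.6.4. Either might name the right baseline. This stands as a limit: the point concerns the wording of 6.3.1.2 and 6.3.2.2, not what was programmed. If the code does use own baseline, text and code disagree and the text still needs correcting.

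**The intent was probably own baseline.** The generic baseline term in 6.4.1.2 and the matching baselines in 6.3.4.2, 6.3.7.2 and 6.3.8 all point that way, and the PSP score is plausibly loose wording under a heading that says change. This is likely, but 6.4.1.2 is the Period 2 model and neither key secondary section cites it. If the authors do swap the baseline silently, the remaining loss is at most the own-only figure: variance ratio 1.10 for PSP and 1.03 for CGI-S.

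**The sizes are assumed.** True, and the 31% needs score, PANSS only and ρ = 0.7 together. The equal-SD assumption for PSP also matters for one column. With s0/s8 of 0.60 to 0.65, the ratio for change with PANSS only falls to about 1.00–1.24. The score column does not move.

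**Keeping both baselines is a preference.** No visible model in the SAP carries two baseline scores. Replacing PANSS would settle the ambiguity, but it is not always a gain: in scenario 2 at ρ = 0.3 the residual variances are 0.910 (own only), 0.840 (PANSS only) and 0.827 (both). Keeping both did no worse than either alone in every scenario.

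**Conclusion.** The concern holds on the readable text. Sections 6.3.1.2 and 6.3.2.2 carry over baseline PANSS and add no own baseline, and 6.3.2.2 names an outcome that contradicts the declared endpoint.

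With complete data, randomization keeps the comparisons unbiased and type I error is not inflated. The primary endpoint is not touched. The cost is precision on two key secondary endpoints: a standard error about 1% to 31% larger for PSP as worded, and 0% to 10% larger for CGI-S (median about 3%). These are illustrations under the stated correlations and SDs. They show that the loss can range from negligible to material, not what it will be in this trial. The second cost is that two readings of the PSP section can give two key secondary results. The point should be fixed, with medium confidence, because the unseen code may already be right.

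**What to change.** Before unblinding:

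- In 6.3.1.2, state that the dependent variable is change from baseline in CGI-S and add baseline CGI-S as a covariate.
- In 6.3.2.2, state that the dependent variable is change from baseline in PSP and add baseline PSP as a covariate. Make both edits together: at ρ = 0.3, correcting the outcome word alone moves the variance ratio from 1.02–1.07 to 1.40–1.68 under equal SDs.
- In both, keep baseline PANSS and the other 6.2.4 covariates.
- Confirm that the Appendix B imputation and analysis models match, and align the PSP outcome and own-baseline covariate with 6.3.8.

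The cost is two sentences of SAP text and a code check. CGI-S and PSP are already collected at baseline (Protocol Appendix B, visit 2), so no new data are needed. SAP 2.6.2 provides for amendments approved before the first database lock.

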6.3.4.1. Definition

The CGI-I scale permits a global evaluation of the patient's overall improvement in symptoms. The CGI-I scale rates the patient's improvement relative to his or her symptoms on a 7-point scale ranging from 1 (very much improved) to 7 (very much worse).

The CGI-I will be administered by the investigator/trained rater at time points specified in the protocol. For this endpoint, change from baseline is not calculated because the scale scores measure change ('improvement') over time. The CGI-I during Periods 1 and 2 will be adjusted to the CGI-S score at the baseline visit (visit 2 in Period 1).

6.3.4.2. Analysis

Least squares mean and least squares means difference at endpoint will be calculated using a mixed model repeated measures (MMRM) analysis will be performed on CGI-I score as the dependent variable, and treatment arm, study visit, treatment-visit interaction, stratification variables (sex and geographic region), age, and CGI-S at baseline as covariates. An unstructured

covariance matrix will be used in all models. Analyses will be performed in SAS using the Kenward-Roger option to estimate the denominator degrees of freedom and standard errors, if convergence problems occur, the steps described in Section 6.2.4 will be employed.

6.3.5. Clinical Global Impression-Severity (CGI-S) scale – At Weeks 1, 2, 4 and 8

Data will be analyzed as described in Section 6.3.1.

6.3.6. Patient Global Impression-Improvement (PGI-I) scale – At Weeks 2, 4 and 8

6.3.6.1. Definition

The PGI-I scale is a 1-item patient-rated instrument that measures improvement of the patient's disease; the patient rates the perceived change in his/her condition in response to therapy (see time points specified in the protocol). It should be noted that for this endpoint, change from baseline is not calculated because the scale scores measure change ('improvement') over time.

The patient is instructed to select a response option on a scale of 1 to 7, where 1=very much better, 2=much better, 3=a little better, 4=no change, 5=a little worse, 6=much worse, 7=very much worse.

6.3.6.2. Analysis

Least squares mean and least squares means difference at endpoints will be calculated using a mixed model repeated measures (MMRM) analysis will be performed on PGI-I score as the dependent variable, and treatment arm, study visit, treatment-visit interaction, stratification variables (sex and geographic region), age as covariates. An unstructured covariance matrix will be used in all models. Analyses will be performed in SAS using the Kenward-Roger option to estimate the denominator degrees of freedom and standard errors, if convergence problems occur, the steps described in Section 6.2.4 will be employed.

6.3.7. Schizophrenia Quality of Life Scale (SQLS) – Change From Baseline to Weeks 4 and 8

6.3.7.1. Definition

The Schizophrenia Quality of Life Scale (SQLS) Revision 4 will be administered at the time points specified in the protocol and will be used to capture quality of life. The 33-item measure yields subscales pertaining to psychosocial and cognition/vitality factors. The items for each subscale are as follows:

- Psychosocial subscale (20 items - Items 3, 4, 5, 6, 8, 10, 11, 13, 15, 16, 17, 18, 19, 21, 22, 24, 25, 27, 29, 30)
- Cognition/vitality subscale (13 items – Items 1, 2, 7, 9, 12, 14, 20, 23, 26, 28, 31, 32, 33).

The items are scored on a five-point scale (1 - never, 2 - rarely, 3 - sometimes, 4 - often, 5 - always). For all items, except the specific 4 items discussed below, higher scores indicate comparatively lower quality of life.

The following four items have reversed scaling and refer to positive aspects of life:

7. I was able to carry out my day-to-day- activities;
12. I felt that I could cope;
14. I slept well;
26. I felt happy.

The above are to be re-coded such as 6 minus recorded score (e.g., 6-ITEM_7) before the scale total is calculated. Individual domain and total scores are standardized by scoring algorithm to a 0 (best health status) to 100 (worst health status) scale, with higher scores indicating comparatively lower quality of life.

Therefore, the total score, namely TS, is calculated as the total of all items minus the number of items answered, divided by the maximum possible total score, namely, and multiplied by 100.

$$TS = \frac{R4S_{tot}}{RS_{max}} \times 100$$

Similarly, each scale score, 'Psychosocial feelings' and 'Cognition and vitality' will be calculated in the same way using the total score and number of items in the scale.

